2.7. Outcomes Assessment Schedule

Baseline assessments are performed prior to randomisation on day 0. Other important assessment time points are detailed below.

Time point (Day)	Activity
0	Enrolment, baseline assessments.
Antibiotic prescription	
0-7	Antibiotic choice(s) is / are checked against respiratory endotracheal tube cultures. If current antibiotic choice(s) is / are not appropriate, primary physicians are advised to switch antibiotic choice according

	
to antibiotic susceptibility report (when there is positive growth) or local microbiology antibiogram (when there is no positive growth).
 
Randomisation to short or long treatment strategy. If randomisation is to short arm, all antibiotics for the participant should be stopped on the day of randomisation (other than, when applicable, anti-tuberculosis antibiotics, prophylaxis e.g. peri or post operative or in immunocompromised hosts, gut prokinetic antibiotics)

0 - discharge	Weekly follow-up for new or changes in antibiotic prescription for all participants.
Outcome assessment	
0 - discharge	
New or changes in antibiotic prescription or new respiratory culture reports will trigger screening for pneumonia recurrence. The US CDC VAP diagnostic criteria will be checked during the preceding week.
 
When these diagnostic criteria are met, two independent respiratory or infectious diseases physicians who are blinded to the randomisation arm will be consulted to verify if the episode is a recurrent episode.

0 - 60	
Mortality is assessed weekly.
 
Secondary outcomes such as adverse events, discharge / readmissions, intubation / extubation, clinical cultures, biochemistry laboratory tests are recorded weekly.

2.8. Data Management Responsibility

An appointed study monitor from the MORU clinical trial support group and a project coordinator will regularly visit the study sites for quality control. All study sites will be assessed prior to initiation of the study for capacity to conduct the randomised controlled trial, during the study and upon completion to ensure data quality. After site initiation, monitoring visits will perform monitoring on informed consent forms, CRF for completeness and accuracy of data and sample storage. There will be a minimum of three monitoring

visits per study site: after 3-5 participants enrolled, after 50% of the target sample size enrolled for a particular site and upon study completion. Monitoring reports will be made available to the study sites and investigators after each visit.

3. QUALITY CONTROL AND DATA VALIDATION

Throughout the trial, data checks will be performed in conjunction with data collection and data entry. Prior to any analysis, the Trial Statistician will perform additional data checks and validations, investigating the data for outliers and inconsistent dates. All apparent outliers will be checked against paper records and either confirmed as valid observations or corrected.

For the final analysis, a manual 100% data entry check of the following variables will be performed by local research staff:

- Dates for enrolment, randomisation, antibiotic durations, discharge, readmissions, intubation and extubations
- Primary outcomes including mortality and pneumonia recurrences
- Secondary outcomes including microbiological cultures, antibiotic susceptibility reports, adverse events

Following this, at least two rounds of queries will be raised by the central data manager based at MORU using the MACRO software to identify possible inconsistencies and missing data.

4. DATA SAFETY MONITORING COMMITTEE AND INTERIM ANALYSES

The data safety and monitoring committee (DSMB) consists of members independent from the study investigator team. The DSMB will review the analysis plan, interim analyses results, and their approval will be required before protocol and analysis plan amendments. The DSMB will receive reports regarding severe adverse events on a monthly basis, and will review the final study report. The DSMB will be empowered to advise stopping or suspending the trial, independent of the study investigators.

DSMB meetings should be held with every interim analysis and extra meetings may be convened at the request of the investigators, sponsor, or DSMB members to discuss emerging data that is a cause for concern. A full interim analysis including all available data from all sites will be reviewed by the DSMB after approximately 25% (125) participants from sites have been recruited and completed their follow-up to review the safety and ethics of the REGARD-VAP trial. Hence there will be four interim analyses will be performed on the primary endpoint.

A trial steering committee will also be constituted and will decide on the continuation of the trial and will report to the central ethics committee. The trial will be terminated if superiority of either short or long treatment durations is shown. We will use the group sequential design adopting the boundaries proposed by Fleming- Harrington- O'Brien ($R=0.8$)⁵ to terminate the trial prematurely once the Z value exceeds the defined boundaries for superiority.

5. DESCRIPTIVE ANALYSIS

5.1. Representativeness of Study Sample and Patient Throughput

A complete CONSORT flow diagram will be included in the trial report, clearly stating the number of patients screened, eligible, randomised and followed-up throughout the trial. Information on reasons for ineligibility will be given; information on randomisations and follow-up will be presented by treatment arm and detail how many participants received their allocated intervention.

5.2. Baseline Comparability of Randomised Groups

For all information collected at baseline, numbers (with percentages) for binary and categorical variables (including sex) and means (and 95% confidence intervals), or medians (with the interquartile range and range) for continuous variables (including baseline patient reported outcomes and age) will be presented overall and by treatment group. There will be no tests of statistical significance or confidence intervals for differences between

randomised groups on any baseline variable because, by definition of randomisation, these arise only due to chance.

5.3. Comparison of Losses to Follow-up

The numbers (with percentages) of losses to follow-up (defaulters and withdrawals) over the 60 days of the study follow-up will be reported and compared between the short and long groups with absolute differences (95% CI). Any deaths (and their causes) will be reported separately within the section on SAEs and complications.

5.4. Description of Available Data

The availability of data for baseline assessments as well as for primary and secondary endpoints will be described for all appropriate trial time points. Data items are defined as available if the case report form has been completed and if the information provided can be used in the analysis. Summaries will be provided overall and by trial arm, and the number of available data items will be presented together with the number of data item expected and a percentage indicating the rate of data compliance for each endpoint and time point (i.e. investigating what percentage of expected data is actually available).

5.5. Description of Adherence with Intervention

Adherence with randomised intervention will be carefully assessed since poor adherence may increase type 1 error.

Adherence in the short arm is defined as all antibiotics being stopped 7 days or fewer from the start date of appropriate antibiotics or VAP respiratory symptom onset date, whichever is later. For example, for a participant who started having respiratory symptoms on 1st March 2020, and who was prescribed an appropriate antibiotic (e.g. meropenem) on 2nd March 2020, day 0 for which antibiotic duration is based on is 2nd March 2020. This participant will be considered adherent if all antibiotics (other than, when applicable, anti-tuberculosis antibiotics, prophylaxis e.g. peri or post operative or in immunocompromised hosts, gut prokinetic antibiotics) are stopped by 9th March 2020. Antibiotics are allowed to

be restarted subsequently for clinical indications. The percentage of participants in the short arm for whom antibiotics are restarted will be reported in the final report.

Adherence in the long arm is defined as antibiotics being continued for more than 7 days from the start date of appropriate antibiotics or VAP respiratory symptom onset date, whichever is later. For example, the same participant who started having respiratory symptoms on 1st March 2020, and who was prescribed an appropriate antibiotic (e.g. meropenem) on 2nd March 2020, day 0 for which antibiotic duration is based on is 2nd March 2020. This participant will be considered adherent if any antibiotics (other than, when applicable, anti-tuberculosis antibiotics, prophylaxis e.g. peri or post operative or in immunocompromised hosts, gut prokinetic antibiotics) are continued on or after 10th March 2020.

Antibiotic durations for the index episode of VAP, calculated using the above descriptions, will be presented in a survival plot to show the distribution of the data. This demonstrates how successful the trial intervention is and no statistical analysis will be performed. Total antibiotic duration, classified by short and long arms, during 60-day follow-up will be analysed as a secondary outcome.

The proportion of participants who are non-adherent will be presented in the CONSORT diagram with a breakdown of the actual reasons.

5.6. Bacterial Pathogens and Antibiotics Used for Treatment

For each index episode of VAP for which the study participants were enrolled for, the associated bacterial pathogen and the initial antibiotic treatment prescribed which were considered appropriate will be presented. These antibiotic regimens will be presented according to bacterial pathogen types and phenotypic resistance patterns (frequency and percentages). Due to the large number of antibiotic treatment choices and pathogen combinations, there will be no subgroup analysis for these combinations.

5.7. Reliability of Outcome Assessment

As it is not possible to completely blind the treating physicians to the antibiotic treatment duration, we have therefore put in measures for an objective measure of study endpoints. Firstly, all participants are followed up on a weekly interval at the same frequency. Secondly, as the primary outcome measure, all-cause mortality is used. As for pneumonia recurrence, independent assessors are blinded to the randomisation arms by only being provided relevant medical notes which do not contain information on the allocated intervention. Cause of mortality will be determined by the local physicians directly.

6. PATIENT GROUPS FOR ANALYSIS

The following patient populations will be utilised in the analysis:

Intention-to-treat (ITT)

The intention-to-treat population includes all study participants who have been randomised during the conduct of the study

Per-protocol

The per-protocol population includes all study participants who fulfill eligibility criteria specified in the inclusion/exclusion criteria, fitness criteria for randomisation and who received 7 days or fewer of appropriate antibiotics in the short arm, and 8 days or more of appropriate antibiotics in the long arm (Section 5.5).

7. ANALYSES TO ADDRESS PRIMARY AIMS

All analyses will be formed with R⁷. All packages used in the analysis will be cited according with the corresponding version numbers. All analysis code will be published in an open access online repository with the final manuscript.

All primary and secondary outcomes of the study populations will be analysed using both unadjusted and adjusted methods in both the PP and ITT populations. The purpose of using both adjusted analyses on the intention-to-treat and per-protocol populations to determine non-inferiority is to minimise the inflation of type 1 error associated with non-adherence in non-inferiority trials⁸.

Multivariable regressions will be performed with inverse probability weighting, using baseline patient characteristics (study site, age, sex, comorbidities, residence prior to admission, type of ICU admitted to, SOFA score, VAP infection with CRE, maximum heart rate and minimum mean arterial blood pressure on randomisation day, duration of intubation prior to developing VAP, reason for intubation, number of days from first respiratory symptom onset to first day of appropriate antibiotics) as independent variables.

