10. STATISTICS AND ANALYSIS

10.1. Description of Statistical Methods for Primary and Secondary Outcomes

Descriptive statistics will include frequency tables for categorical data, means (SDs), or medians (interquartile ranges) depending on the distribution of the data. Categorical variables will be compared with χ^2 and Fisher exact tests as appropriate and continuous variables with unpaired, 2-tailed t tests or nonparametric Wilcoxon rank sum tests as appropriate.

The primary and secondary outcomes of the study populations will be analyzed using both unadjusted and adjusted methods in both the per-protocol and intention-to-treat populations. Adjustment will be done with inverse probability weighting, using baseline patient characteristics (study site, age, gender, comorbidities, residence prior to admission, type of ICU admitted to, SOFA score, VAP infection with CRE, maximum heart rate and minimum mean arterial blood pressure on randomisation day, duration of intubation prior to developing VAP, reason for intubation, number of days from first respiratory symptom onset to first day of appropriate antibiotics) as independent variables.

Subgroup analysis will be performed using the primary outcome as the dependent variable amongst patients with VAP caused by Gram-negative non-fermenters and carbapenem-resistant bacilli. VAPs caused by Gram-negative non-fermenters have been previously shown to be associated increased recurrence [10,11]. VAPs caused by carbapenem-resistant bacilli have no standardised treatment. This will be exploratory as the sample sizes for each of this groups will not reach adequate power.

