7.2. Statistical Methods Used for Analysis of Primary Outcome

Based on both the ITT and PP population, the proportions of participants experiencing the primary endpoint will be tabulated by treatment group. If the absolute, upper two-sided 90% CIs around the absolute unadjusted difference is less than 12%, then the criteria of non-inferiority will be met.

A multivariable logistic regression model, will be applied on the ITT population to calculate the estimates of the treatment differences adjusted for baseline patient characteristics described above. Categories with low counts may be combined. For example, in the event of comorbidities with very low counts, these comorbidities may be combined to avoid difficulties with the maximum likelihood estimation of the logistic model. Where no

information has been entered on the comorbidities, the participants will be considered not to suffer from these comorbidities.

For the PP population, inverse probability weighting⁹ will be applied to calculate the estimates of the treatment differences using the same baseline patient characteristics as above.

For these multivariate logistic regression models, residual and predicted values produced from the model will be examined to assess the assumptions of the model. Specifically, the assumption of linearity between the predicted log odds and the covariates is assessed by plotting lowess graphs. The independence of the error terms will be considered. Influential cases are investigated by plotting the standardised Pearson's residuals against the predicted probabilities and the leverage of the individual observations.

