7.5. Pre-specified Subgroup Analysis

All subgroup analyses will be based on the ITT population, and presented as forest plots.

Subgroup analysis will be performed using the primary outcome as the dependent variable amongst patients with VAP caused by Gram-negative non-fermenters and carbapenem-resistant bacilli. Gram-negative non-fermenting bacilli include *Pseudomonas* spp., *Acinetobacter* spp., and *Stenotrophomonas* spp.. Carbapenem-resistant bacilli are Gram-negative bacteria which are resistant to at least one agent from the carbapenem category of antibiotics. VAPs caused by Gram-negative non-fermenters have been previously shown to be associated with increased recurrence^{12,13}. VAPs caused by carbapenem-resistant bacilli have no standardised treatment. This will be exploratory as the sample sizes for each of these groups will not reach adequate power.

Subgroup analysis will be performed with tests for interaction, where multivariable logistic regression models will be constructed with the occurrence of the primary endpoint as the outcome, and the randomised treatment as well as VAP caused by Gram-negative non-fermenters and carbapenem-resistant bacilli and the interaction between randomised treatment and pathogen type as explanatory variables. Odds ratio from the interaction tests will be presented with 95% CI and corresponding p-values.

For all pre-specified subgroup analyses, diagnostic checks will be performed as described in section 7.2.

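### The per-protocol weights carry one undefined pathogen term (CRE) and omit non-fermenters, which leaves a risk of residual confounding if adherence differs by pathogen and arm

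*SAP*

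**What the plan says.** Protocol 10.1 and SAP 7 give the same list of baseline characteristics for adjustment. The item that concerns the pathogen is "VAP infection with CRE"; in the SAP it stands in the run "SOFA score, VAP infection with CRE, maximum heart rate and minimum mean arterial blood pressure on randomisation day". No other item describes the organism, and neither abbreviation list explains CRE.

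SAP 7.2 uses the list twice: in the logistic model for the ITT population, and in the PP population, where inverse probability weighting "will be applied to calculate the estimates of the treatment differences using the same baseline patient characteristics as above".

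Pathogen type appears elsewhere only as an exploratory subgroup factor. SAP 7.5 defines the groups: "Gram-negative non-fermenting bacilli include *Pseudomonas* spp., *Acinetobacter* spp., and *Stenotrophomonas* spp", and "Carbapenem-resistant bacilli are Gram-negative bacteria which are resistant to at least one agent from the carbapenem category of antibiotics". These subgroup analyses are confined to the ITT population, and SAP 7.7 plans no further sensitivity analysis.

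On prognosis, Protocol 10.1 states that "VAPs caused by Gram-negative non-fermenters have been previously shown to be associated increased recurrence". Of carbapenem-resistant bacilli it says only that treatment is not standardised. Protocol 3 says non-fermenters cause the majority of VAP in the region, but adds that the earlier recurrence signal was non-significant and might be spurious.

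**The concern.** The PP population is selected after randomisation on antibiotic days received (SAP 6), and those days are counted from the first coverage matched to a pathogen's susceptibility (SAP 2.4). The earliest stopping day in the short arm also depends on whether cultures are positive. Culture results usually arrive 48 to 72 hours after sampling (Protocol 7.7), so at randomisation the treating team will usually know the organism, and they are told the allocation once the stop criteria are met. It is plausible that they depart from the short allocation more often for a non-fermenter, and from the long allocation more often for an easier organism or a negative culture.

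If non-fermenters also carry a higher risk of death or recurrence, the short PP arm loses high-risk participants and the long PP arm keeps them, which tilts the comparison towards non-inferiority. SAP 5.5 and SAP 7 rely on the PP analysis, alongside ITT, to limit the type I error that non-adherence causes. A weight model can correct only for the variables it contains. CRE in its usual sense covers Enterobacterales, so it would miss both non-fermenters and most of the carbapenem resistance that the protocol describes (95% of *A. baumannii* and 75% of *P. aeruginosa* isolates in Thailand).

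**Working it through.** **1. The plan's own figure.** With 55% v 67%, one-sided 5% and 80% power, the pooled two-proportion formula gives n = [1.645·√(2×0.61×0.39) + 0.842·√(0.55×0.45 + 0.67×0.33)]² / 0.12² = 203.2. That is 204 per arm, 408 in total. A simulated group-sequential inflation of about 1.015 gives 414, against the stated 412. 412/0.9 = 458, consistent with 460. The point does not dispute the sample size; 206 evaluable per arm is used below.

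**2. Inputs that the documents do not give (assumptions).** Non-fermenter share q = 0.60 (the protocol says only a majority). Outcome risk higher by g = 5 to 15 points in non-fermenters. CRE in 20% of the remainder, i.e. 8% of all. True effect zero for the bias. Adherence in non-fermenters v others:
- none: unrelated to pathogen
- mild: short 90% v 95%, long 95% v 95%
- moderate: short 80% v 95%, long 98% v 90%
- strong: short 60% v 95%, long 98% v 80%

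**3. Unweighted PP bias.** With adherence a1 in non-fermenters and a0 in others, the non-fermenter share among adherers in an arm is f = q·a1 / (q·a1 + (1-q)·a0). Bias = g × (f_short - f_long). Strong pattern: f_short = 0.36/(0.36+0.38) = 0.4865; f_long = 0.588/(0.588+0.32) = 0.6476; difference -0.1611. With g = 0.15 the bias is -2.42 points.

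**4. Bias left after weighting on CRE alone.** The weights restore the 8%/92% split by CRE, but not the mix within the 92% (60 non-fermenter, 32 other). The weighted share is 0.92 × 0.60·a1 / (0.60·a1 + 0.32·a0). Strong pattern: short 0.92×0.36/0.664 = 0.4988; long 0.92×0.588/0.844 = 0.6410; difference -0.1422. With g = 0.15 the bias is -2.13 points. A simulation of 2,000,000 patients gave -2.15. CRE removes about a tenth of the bias (1 - 0.1422/0.1611 = 12%).

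**5. With a non-fermenter term in the weights.** Each arm's share returns to q and the bias is zero by construction. The simulation gave values within about 0.1 point of zero in every pattern.

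**6. PP-only type I error at the 12-point margin (unweighted).** Error = Φ(-bias/SE - 1.645), with SE = √(0.67×0.33/n_short + 0.55×0.45/n_long). Strong pattern: n_short = 206×0.74 = 152; n_long = 206×0.908 = 187; SE = 0.0527. With g = 0.15: 0.0242/0.0527 = 0.459, and Φ(-1.186) = 11.8%.

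| Adherence pattern | Unweighted bias, g = 5 to 15 points | CRE-only weighted bias | Unweighted PP-only error |
|---|---|---|---|
| None | 0 | 0 | 5.0% |
| Mild | -0.1 to -0.2 | -0.1 to -0.2 | 5.1% to 5.4% |
| Moderate | -0.3 to -0.9 | -0.3 to -0.8 | 5.7% to 7.2% |
| Strong | -0.8 to -2.4 | -0.7 to -2.1 | 6.8% to 11.8% |

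Putting the residual -2.13 points into the same formula gives Φ(0.0213/0.0527 - 1.645) = Φ(-1.24) = 10.7%, without allowing for the extra variance from weighting. Changing q matters little: in the strong pattern with g = 0.15, the unweighted bias is -2.45 at q = 0.5 and -2.18 at q = 0.7.

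**The case against.** A reader might infer that the PP analysis is confounded as it stands. The documents do not show that. The bias needs pathogen to affect adherence differently in the two arms and also to affect the outcome, and no adherence by pathogen is reported. Some features point to limited pathogen-driven departures: SAP 2.7 has short-arm antibiotics stopped on the day of randomisation, and Protocol 12.2 has the study team contact primary physicians beforehand to secure adherence. If adherence is unrelated to pathogen the bias is zero, and the direction rests on the assumed pattern. This stands, and it limits the point to a risk.

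A reader might also infer that the plan ties carbapenem resistance to recurrence. It does not; it makes that link for non-fermenters only, and Protocol 3 doubts even that. The doubt lowers the expected size of the bias but is no reason to leave the variable out.

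The other covariates (site, SOFA score, ICU type, duration of intubation before VAP, days to appropriate antibiotics) may partly stand in for pathogen. Their contribution was not modelled, so the weighted figures above may be too large.

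If CRE was meant to cover all carbapenem-resistant Gram-negatives, the gap on resistance closes. The non-fermenter omission remains.

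Finally, SAP 7.2 states the non-inferiority criterion on the unadjusted difference, so better weights would not change that test. They act through Protocol 10.1, which requires the adjusted analyses to meet the margin as well. This is correct, and it is a conflict that the plan should settle.

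**Conclusion.** The point holds as a conditional weakness in the PP weighting set and should be corrected. The omission is plain on the text. Its effect is not established: under the assumptions shown, the bias runs from 0 to about -2 points in favour of the short arm, and PP-only type I error from 5% to about 12%. The upper figures need strongly pathogen-dependent adherence together with a 15-point risk gap, and the tabulated error rates are for the unweighted PP difference. Non-inferiority also has to be met in ITT, so the error of the joint decision is lower than the PP-only figure.

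It would be wrong to extend the point to ITT. Randomisation protects that comparison from pathogen imbalance, and the missing terms cost at most some precision there.

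**What to change.** - Define CRE in Protocol 10.1 and SAP 7.
- Add to the PP weighting set in SAP 7.2: non-fermenter yes/no (SAP 7.5 definition), culture-negative yes/no, and carbapenem-resistant Gram-negative yes/no (SAP 7.5 definition). State that a mixed culture containing any non-fermenter counts as non-fermenter.
- Report adherence by pathogen group and arm, so that readers can see whether the condition for bias was met.
- In the ITT model the same terms are optional.
- State in both documents whether non-inferiority is judged on the unadjusted difference alone or on the unadjusted and adjusted estimates together.

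Cost: two or three extra model terms, and an amendment that needs DSMB approval under SAP 4. No new data should be needed, because SAP 5.6 already has the pathogen and resistance pattern of each index episode reported. The trial statistician is unblinded (SAP 9.2), so the terms should be fixed before outcome data are analysed.
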